## **9.15 Participant Withdrawal Criteria**

The following pre-randomisation withdrawal criteria will apply:

1. Subject/guardian is unable to demonstrate safe use of study insulin pump and CGM as judged by the investigator
2. Subject/guardian fails to demonstrate compliance with insulin pump and CGM during run-in

The following pre- and post-randomisation withdrawal criteria will apply:

3. Subjects/guardians may terminate participation in the study at any time without necessarily giving a reason and without any personal disadvantage
4. Significant protocol violation or non-compliance
5. Any severe hypoglycaemia event related to the use of the closed loop system
6. Two severe hypoglycaemia events not related to the use of the closed loop system
7. DKA unrelated to infusion site failure and related to the use of the closed loop system
8. Decision by the investigator or the sponsor that termination is in the subject's best medical interest
9. Allergic reaction to insulin
10. Allergic reaction to adhesive surface of infusion set or glucose sensor

Efforts will be made to retain subjects in follow up for the final primary endpoint assessment even if the intervention is discontinued, unless the investigator believes that it will be harmful for the subject to continue in the trial. Subjects/guardians who are withdrawn for reasons stated in (4) to (10) will be invited to provide a blood sample at the end of the planned study intervention for the assessment of HbA1c.

Subjects/guardians who discontinue study intervention prior to the final visit will receive an exit survey and may be invited for an interview.

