## **12.3 Questionnaires**

Quantitative data on health-related quality of life will be assessed using validated questionnaires. Parents/guardians will complete a series of validated questionnaires at baseline and at the end of each study arm. In the extension phase parents/guardians will complete the same series of validated questionnaires at the end of the extension phase, 18 months after the primary phase final study visit (UK sites only). It is estimated that parents/guardians will take 15-25 minutes to complete the surveys. All results will be evaluated at the end of the study. All questionnaires are available in English, French and German

**Table 10 – Questionnaires to be completed by parents/guardians at baseline, at the end of each intervention arm (Visit 1, 6, and 8) and at the end of the extension phase (Visit 9).**

Measure	Construct Measured / Relevant Points	Duration
Strengths and Difficulties Questionnaire (SDQ) (61)	This is a widely used 25 item self-report inventory behavioural screening questionnaire for children and adolescents. The same 25 items are included in questionnaires for completion by the parents.	5-10 min
Hypoglycaemia Fear Survey (HFS) Parents of Young Children (62-64)	Validated questionnaire to measure several dimensions of fear of hypoglycaemia. It consists of a “Behaviour subscale” that measures behaviours involved in avoidance and over-treatment of hypoglycaemia and a “Worry subscale” that measures anxiety and fear surrounding hypoglycaemia.	5- 10 min
WHO Well-Being Index (WHO-5) (65)	Widely used 5-item questionnaire assessing subjective psychological well-being.	2-3 min
Epworth sleepiness scale (ESS) (66)	Simple 8-item questionnaire to measure the parents general level of daytime sleepiness and average sleep propensity in daily life.	3-5 min
Insulin delivery Systems: Perceptions, Ideas, Reflections, and Expectations (INSPIRE) Survey	Measures the psychological side of automated insulin delivery. Child version has 27 items; Parent version has 30 items.	5-10 min
Pittsburgh Sleep Quality Index (PSQI)	The PSQI is a 19 item questionnaire that holistically assesses sleep quality and sleep duration.	5-10 min (Visit 8 only)
Children's Sleep Habit Questionnaire (CSHQ)	The CSHQ is a validated retrospective 45-item questionnaire that examines sleep behaviour in young children.	10-15 min (Visit 8 only)

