## **14.12 Sample Size and Power Calculations**

The study will run at seven sites. We have ensured adequate recruitment of participants and centres by allowing for a potential 50% uptake and 10% drop-out of participants among collaborative paediatric sites, with further contingency sites including participant identification sites (identified but not included as applicants).

Data from the SENCE study (NCT02912728) were used to estimate the standard deviation of the primary endpoint. Only subjects from the two treatment arms involving CGM use in this study who were using an insulin pump at the time of enrolment were used to estimate the SD. Based on data from this study, 65 subjects are required to attain 90% power to detect a difference if a treatment effect of 5%, a standard deviation of 10.3% for an individual measurement, and a correlation of 0.3 between periods are assumed. Adding an additional 10% to this sample size to account for drop outs results in a final sample size of 72 subjects.

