161 treatment intervention. Summary statistics also will be tabulated for the primary outcome during  
162 the extension phase. For the main study, the treatment interventions will be compared using a  
163 linear mixed model adjusting for period as a fixed effect and site as a random effect. The analysis  
164 dataset will be three records per subject (one for baseline and one for each period). Inclusion of  
165 the pre-randomization baseline value as a third observation for each subject in the model gives a  
166 variance reduction analogous to adjusting for it as a covariate. Baseline is not modeled as a  
167 covariate in this analysis because there is no corresponding baseline for period 2, only pre-  
168 randomization. Note that adjusting for a post-randomization period 2 baseline can introduce a  
169 bias so that is not done here. The model will account for correlated data from the same subject.  
170 A 95% confidence interval will be reported for the difference between the interventions based on  
171 the linear mixed model.

172 Residual values will be examined for an approximate normal distribution. If values are highly  
173 skewed, then a ranked normal score transformation will be used instead. However, previous  
174 experience suggests that the primary outcome will follow an approximately normal distribution.  
175 A separate model will also be built with the inclusion of a period by treatment interaction to  
176 assess for the presence of a carryover effect. We do not expect a carryover effect to be present. A  
177 two-sided p-value will be reported.

178 For the primary endpoint and other key endpoints listed in section 4, the familywise type I error  
179 rate (FWER) will be controlled at two-sided  $\alpha = 0.05$ . A gatekeeping strategy will be used, where  
180 the primary endpoint will be tested first, if passing the significance testing, other key endpoints  
181 will be tested in the order listed below using the fixed-sequence method at  $\alpha = 0.05$ :

- 182 • Time spent with sensor glucose levels between 3.9 to 10.0 mmol/l
- 183 • Time spent above target glucose (10.0 mmol/l)
- 184 • HbA1c

185     • Average of glucose levels  
 186     • Time spent below target glucose (3.9 mmol/l)

187 This process continues iteratively moving to the next variable down on the list until a non-  
 188 significant result ( $p \geq 0.05$ ) is observed, or all five variables have been tested. If a non-  

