280 similar trend to the overall treatment effect is seen in the different times of day.

281 The study is not expected to have sufficient statistical power for definitive conclusions in the  
282 secondary analyses by time of day, and statistical power will be low to formally assess for the  
283 presence of a treatment by time of day interaction. Interpretation of the analyses by time of day  
284 will depend on whether the overall analysis demonstrates a significant treatment effect. In the  
285 absence of any significant treatment effects in the overall analyses, assessment of secondary  
286 analyses by time of day will be considered exploratory and used to suggest hypotheses for  
287 further investigation in future studies.

288 **7.6 Questionnaire Analyses**

289 For each questionnaire (and their corresponding subscales), total scores will be calculated and  
290 reported at each time point. They will also be compared between treatment arms using the same  
291 model described above for the primary outcome. The distribution of responses for each

292 individual question at baseline and for each treatment arm will also be reported in separate  
293 tables.

294 For the INSPIRE Survey, a mean score will be calculated instead of a total score. The mean  
295 score will be calculated after excluding all questions where the participants give a response of  
296 "NA".

297 For the Pittsburgh Sleep Quality Index (and all of its subscales), the scoring instructions will be  
298 used to calculate the total scores overall and by subscale. For this questionnaire, scores will be  
299 tabulated for each parent who completes the survey.

300 For the INSPIRE Survey and the CL Experience Survey, a treatment arm comparison will not be  
301 done, because the surveys are only completed at the end of the CL arm. For these questionnaires,  
302 only summary statistics for the scores and the distribution of responses for each question will be  
303 reported. Additionally, treatment arm comparisons will not be done for the Pittsburgh Sleep  
304 Quality Index or the Children's Sleep Habit Questionnaire, because they are only completed at  
305 visit 8.

306 For the Strengths and Difficulties Questionnaire, no overall total score will be calculated that  
307 involves every question. Instead, only a Total Difficulties Score is computed from the questions  
308 comprising the Emotional Problems, Conduct Problems, Hyperactivity, and Peer Problems  
309 subscales.

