310 The electronic data capture system for this study will not allow the subject to submit any  
311 questionnaires until all items are completed. Analysis will be limited to subjects who submit a  
312 questionnaire (no imputation).

313 **7.7 Ancillary Analyses**

314 Cost utility analyses and human factors analyses will be described in a separate document.

315 **8. Safety Analyses**

316 All safety outcomes will be tabulated by participant for all events from enrollment to the final  
317 study visit.

318 **8.1 Definitions**

319 Reportable adverse events for this protocol include any untoward medical occurrence,  
320 unintended disease or injury, or untoward clinical signs (including abnormal laboratory findings)  
321 in a subject who has received an investigational device, whether or not related to the  
322 investigational medical device. These include severe hypoglycemia (SH) and diabetic  
323 ketoacidosis (DKA).

324 Hypoglycemic events will be considered severe if the event requires assistance of another person  
325 due to altered consciousness to actively administer carbohydrate, glucagon, or other resuscitative  
326 actions. This means that the subject is impaired cognitively to the point that he/she is unable to  
327 treat him- or herself, is unable to verbalize his or her needs, is incoherent, disoriented, and/or  
328 combative, or experiences seizure or coma. If plasma glucose measurements are not available  
329 during such an event, neurological recovery attributable to the restoration of plasma glucose to

330 normal is considered sufficient evidence that the event was induced by a low plasma glucose  
331 concentration.

332 Definite DKA is defined as having all of the following:

- 333 • Hyperglycemia (blood glucose >200 mg/dL or >11 mmol/L)
- 334 • with either low pH (<7.3) or low serum bicarbonate (<15 mmol/L)
- 335 • and ketonemia or ketonuria

336 **8.2 Adverse Events Summary**

337 All episodes of SH and of DKA along with any other reportable adverse events will be listed by  
338 treatment group.

339 Separate listings will be provided for pre-randomization and post-randomization adverse events.  
340 A separate listing also will be provided for events that occur during the extension phase.

341 **8.3 Comparison of Safety Outcomes between Treatment Groups**

342 The following safety analyses will be performed if enough events occur for formal statistical  
343 analyses.

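### No validated questionnaire is scheduled when a family stops early, so a family that leaves follow-up during an arm has no score for that arm

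*Combined protocol and SAP*

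**What the plan says.** **Schedule.** Protocol 12.3 states: "Parents/guardians will complete a series of validated questionnaires at baseline and at the end of each study arm". In the primary phase these are Visits 1, 6 and 8 (Table 10). Visit 9 applies only to the UK extension.

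**Early stopping.** Protocol 9.15 names four things sought after stopping.
- Continued follow-up for one purpose: "Efforts will be made to retain subjects in follow up for the final primary endpoint assessment even if the intervention is discontinued", unless the investigator thinks continuing would be harmful.
- HbA1c: families withdrawn for reasons 4 to 10 "will be invited to provide a blood sample at the end of the planned study intervention for the assessment of HbA1c".
- An exit survey, and possibly an interview: "Subjects/guardians who discontinue study intervention prior to the final visit will receive an exit survey and may be invited for an interview".

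The validated questionnaires are not on this list.

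**Analysis.** SAP 7.6 says of questionnaire scores: "They will also be compared between treatment arms using the same" model as the primary outcome. In SAP 6.3 that is a linear mixed model whose "dataset will be three records per subject (one for baseline and one for each period"). On missing forms, SAP 7.6 says: "Analysis will be limited to subjects who submit a" questionnaire, without imputation. It makes no arm comparison for INSPIRE, the closed loop experience survey, the Pittsburgh index or the children's sleep questionnaire. Four instruments remain for comparison: Strengths and Difficulties, Hypoglycaemia Fear, WHO-5 and Epworth. SAP 13.2 treats them as secondary and applies a false discovery rate adjustment.

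**Dropout.** Protocol 14.12 arrives at 72 by "Adding an additional 10% to this sample size to account for drop outs".

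**The concern.** The four compared questionnaires measure how families respond to living with each treatment. A family that leaves because of burden, alarms or worry is likely to have scored the arm it left poorly, and that score is the one not collected. If such families leave one arm more than the other, that arm looks better than it was.

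Unequal leaving is possible here. Two of the withdrawal criteria in 9.15 concern events related to closed loop use, so they can be met only where closed loop is in use. (The criteria themselves are not at issue.) A severe hypoglycaemia event might well raise the Hypoglycaemia Fear score that would then be missing.

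Other endpoints have more protection. Protocol 9.15 seeks follow-up data after stopping for the primary endpoint and HbA1c, and SAP 7.2 gives a likelihood method for missing HbA1c and BMI scores. The questionnaires have no collection rule at stopping and no sensitivity analysis for missing scores.

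**Working it through.** **1. The plan's own figures.** Inputs from protocol 14.12: difference 5 points, SD 10.3, correlation 0.3 between periods, 90% power. Alpha is two-sided 0.05 (14.2).
- SD of the within-child difference = 10.3 × √(2 × (1 − 0.3)) = 12.19.
- Normal approximation: n = ((1.960 + 1.282) × 12.19 / 5)² = 62.4, so 63.
- Noncentral t: power is 89.8% at n = 64 and 90.3% at n = 65, which gives the plan's 65.
- 65 × 1.10 = 71.5, so 72.

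The allowance is therefore 72 − 65 = 7 families over the whole trial (9.7%).

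**2. Scores lost.** Complete data would be 2 × 72 = 144 end-of-arm scores. Assume 7 families leave follow-up altogether.

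| When they leave | What each still contributes | Scores under the plan | With a form at stopping, at most |
|---|---|---|---|
| All in period 1 | baseline | 144 − 14 = 130 | 137 |
| All in period 2 | baseline and period 1 | 144 − 7 = 137 | 144 |

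**3. Size of a possible bias.** The documents give no score for leavers. Assume they score 0.5 to 1 SD worse than stayers in the arm they left and the same as stayers in the other arm.
- All 7 from one arm: bias = 7/72 × 0.5 = 0.049 SD, up to 7/72 × 1 = 0.097 SD.
- SE of the paired difference with 72 pairs, borrowing the 0.3 correlation from time in range: √(2 × 0.7 / 72) = 0.139 SD.
- Ratio: 0.049/0.139 = 0.35, up to 0.097/0.139 = 0.70 SE.
- With the 65 complete pairs: SE = √(1.4/65) = 0.147 SD, and the ratio is 0.33 to 0.66.
- Leavers split evenly between arms with similar deficits: both arm means shift by about the same amount, the difference is nearly unbiased, and the loss is mainly precision.

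**4. Does the three-record model repair this?** An illustrative simulation used 600 replicates of 72 families, half in each order. Assumptions: true effect 0.3 SD, correlation 0.3 or 0.5 treated as known, and 7 families leaving during closed loop with no later scores. It omits the site effect.

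| Leaving depends on | Three-record model | Stayers only |
|---|---|---|
| Baseline score | 0.29 to 0.30 | 0.29 to 0.30 |
| Unseen closed loop score (strongly) | 0.39 to 0.44 | 0.38 to 0.42 |

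In the first case there is essentially no bias. In the second the model overstates the effect by 0.09 to 0.14 SD, about as much as an analysis of stayers alone. The planned data cannot show which case applies.

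**The case against.** The case against a stronger reading is good, and most of it stands.

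- A reader might infer that the exit survey replaces the questionnaires. Protocol 9.15 does not say so. Stopping the intervention is not leaving the study, and a retained family could still complete the forms at Visit 6 or 8b. But the retention sentence names only the primary endpoint, so nothing asks for this.
- A reader might infer that the comparison covers only families who stayed. It does not. The mixed model accepts incomplete records, and the SAP's limit to submitted forms does not require both periods. A family leaving in period 2 contributes baseline and period 1.
- A reader might take the 10% as expected questionnaire loss in each arm. It is a sample-size allowance for the whole trial.
- The exit survey's content and timing are not described, and SAP 7.7 puts human factors analyses in a separate document. One cannot say the survey goes unused. Interviews and actigraphy also serve the human factors objective.
- The size in step 3 needs every leaver in one arm and an assumed deficit, and stays below one SE.
- A score taken at stopping, perhaps after a few days of use, is not the week 16 outcome. Making it the main result would be debatable.

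None of this supplies a score for a family that leaves follow-up during an arm, and step 4 shows that the model is no safeguard when leaving depends on that score.

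**Conclusion.** The point holds in a limited form. No validated questionnaire is scheduled at early stopping, and none is sought afterwards, so a family that leaves follow-up mid-arm has no score on the four compared instruments for that arm. The possible bias is about 0.05 to 0.10 SD (0.35 to 0.70 SE). That rests on three assumptions: all 7 leavers come from one arm, they score 0.5 to 1 SD worse there, and the 0.3 correlation for time in range carries over to questionnaires. With balanced leaving and similar deficits, little bias remains. The primary endpoint and the tested hierarchy are unaffected. This is a cheap improvement to secondary outcomes and does not invalidate the comparison.

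**What to change.** **Protocol 9.15 and 12.3.** Offer the four questionnaires compared between arms at discontinuation, alongside the exit survey. State also that families who stop the intervention but stay in follow-up are asked to complete them at the scheduled Visit 6 or 8b.

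**SAP 7.6.** Keep scheduled-visit scores as the main analysis. Add a sensitivity analysis that takes the discontinuation score as that arm's value, under the assigned treatment, where no scheduled score exists.

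**Cost.** About a sentence in each of the three sections, plus 15 to 25 minutes (the estimate in 12.3 for the series) for about 7 families. Some will decline, and the scores will be taken before week 16, which is why they belong in the sensitivity analysis. A period 1 leaver will still have no score for the second arm.

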## **9.16 Study stopping criteria**

The study may be stopped if three consecutive participants withdraw on safety grounds or on the advice of an independent Data Safety Monitoring Board (DSMB).

## **9.17 Co-enrolment Guidelines**

To avoid potentially confounding issues, ideally participants should not be recruited into other trials. Where recruitment into another study is considered to be appropriate and without having any detrimental effect on the present study, this must first be discussed with the Chief Investigator, or the Sponsor or its representative.

### *Germany only*

Participants will not be recruited into other trials and patients currently participating in other interventional clinical trials will be excluded from participation in KidsAP02.

## **9.18 Support Telephone Line**

There will be a 24-hour telephone helpline to the local research teams for subjects/guardians in case of any technical device or problems related to diabetes management such as hypo- or hyperglycaemia (primary phase only). The local research team will have access to central 24 hour advice on technical issues (primary phase only).

## **9.19 Subject Reimbursement**

The study will provide the CGM device, insulin pump, closed loop components and related consumables for the primary study phase. For the extension phase, the study will provide the closed loop app and the host device (Android phone), and insulin pump. Glucose meters and glucose test strips will also be provided where required. A study payment will be made to reflect local practice. The amount paid will be specified in the participant information sheet/informed consent form and REC application form. Reasonable travel expenses will also be reimbursed. After completing the study, subjects/guardians will not keep the study devices. They will revert to their conventional insulin pump therapy.

# 10 Endpoints

## 10.1 Primary Endpoints

The primary endpoint is the between group difference in time spent with sensor glucose levels between 3.9 to 10.0 mmol/l (70 to 180 mg/dl) during the 4 months intervention period.

## 10.2 Other Key Endpoints

- Time spent above target glucose (10.0 mmol/l) (180 mg/dl)
- HbA1c
- Average of glucose levels
- Time spent below target glucose (3.9 mmol/l) (70 mg/dl)

## 10.3 Secondary Endpoints

Secondary endpoints include:

- Standard deviation, and coefficient of variation of glucose levels
- Time with glucose levels <3.0 mmol/l (54 mg/dl)
- Time with glucose levels in significant hyperglycaemia (glucose levels > 16.7 mmol/l) (300 mg/dl)
- AUC of glucose below 3.5 mmol/l (63 mg/dl)
- BMI SDS
- Total, basal, and bolus insulin dose

Endpoints regarding glucose levels will be based on sensor glucose data.

## 10.4 Safety Evaluation

Safety evaluation will comprise the number of episodes of severe hypoglycaemia as well as the number of subjects experiencing severe hypoglycaemia, frequency of diabetic ketoacidosis, and other adverse events or serious adverse events.

All subjects including those who withdraw will be included in the safety evaluation.

